12 ADVERSE EXPERIENCE REPORTING AND DOCUMENTATION

12.1 Adverse Events

An adverse event (AE) is any untoward medical occurrence in a clinical investigation of a patient administered a pharmaceutical product and that does not necessarily have a causal relationship with the treatment. An AE is therefore any unfavorable and unintended sign (including an abnormal laboratory finding), symptom or disease temporally associated with the administration of an investigational product, whether or not related to that investigational product. An unexpected AE is one of a type not identified in nature, severity, or frequency in the current Investigator's Brochure or of greater severity or frequency than expected based on the information in the Investigator's Brochure.

The Investigator will probe, via discussion with the subject, for the occurrence of AEs during each subject visit and record the information in the site's source documents. Adverse events will be recorded in the patient CRF.

AE Severity

The National Cancer Institute's Common Terminology Criteria for Adverse Events (CTCAE) in Table 1 should be used to assess and grade AE severity, including laboratory abnormalities judged to be clinically significant. If the experience is not covered in the CTCAE, the guidelines shown in Table 2 below should be used to grade severity. It should be pointed out that the term "severe" is a measure of intensity and that a severe AE is not necessarily serious. $K+ > 6.0$ will be considered an adverse event. $K+ < 6.0$ will be considered an expected side effect of the medication. As previously described, all $K+ > 5.0$ will be treated according to the hyperkalemia protocol.

Table 1. National Cancer Institute's Common Terminology Criteria for Adverse Events

Severity (Toxicity Grade)	Description
Grade 1, Mild	Mild; asymptomatic or mild symptoms; clinical or diagnostic observations only; intervention not indicated.
Grade 2, Moderate	Moderate; minimal, local or noninvasive intervention indicated; limiting age-appropriate instrumental ADL*.
Grade 3, Severe	Severe or medically significant but not immediately life-threatening; hospitalization or prolongation of hospitalization indicated; disabling; limiting self care ADL**.
Grade 4, Life-threatening	Life-threatening consequences; urgent intervention indicated.
Grade 5, Death	Death related to AE.

Table 2. AE Severity Grading

Severity (Toxicity Grade)	Description
Mild (1)	Transient or mild discomfort; no limitation in activity; no medical intervention or therapy required. The subject may be aware of the sign or symptom but tolerates it reasonably well.
Moderate (2)	Mild to moderate limitation in activity, no or minimal medical intervention/therapy required.
Severe (3)	Marked limitation in activity, medical intervention/therapy required, hospitalizations possible.
Life-threatening (4)	The subject is at risk of death due to the adverse experience as it occurred. This does not refer to an experience that hypothetically might have caused death if it were more severe.

AE Relationship to Study Drug

The relationship of an AE to the study drug should be assessed using the following the guidelines in Table 3.

Table 3. AE Relationship to Study Drug

Relationship to Drug	Comment
Definitely	Previously known toxicity of agent; or an event that follows a reasonable temporal sequence from administration of the drug; that follows a known or expected response pattern to the suspected drug; that is confirmed by stopping or reducing the dosage of the drug; and that is not explained by any other reasonable hypothesis.
Probably	An event that follows a reasonable temporal sequence from administration of the drug; that follows a known or expected response pattern to the suspected drug; that is confirmed by stopping or reducing the dosage of the drug; and that is unlikely to be explained by the known characteristics of the subject's clinical state or by other interventions.
Possibly	An event that follows a reasonable temporal sequence from administration of the drug; that follows a known or expected response pattern to that suspected drug; but that could readily have been produced by a number of other factors.
Unrelated	An event that can be determined with certainty to have no relationship to the study drug.

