3.1.1.1 Common Side Effects

- Hyperkalemia: We anticipate that approximately 1% of patients may develop serious hyperkalemia that may warrant discontinuation. However this may be considerably higher in patients with GFR of 40-50 ml/minute who will constitute a minority of the patients in the trial.
- Increases in BUN and creatinine

- Hypomagnesemia
- Gynecomastia or breast discomfort. Gynecomastia is a well-described adverse effect of spironolactone and is related to dose and duration of treatment; we anticipate that approximately 10% of patients may develop gynecomastia that may warrant discontinuation. Generally, discontinuation of treatment results in resolution of gynecomastia.

3.1.1.2 *Other Side Effects*

- Cardiovascular: Vasculitis
- Central nervous system: Ataxia, confusion, drowsiness, headache, lethargy
- Dermatologic: Erythematous maculopapular rash, Stevens-Johnson syndrome, toxic epidermal necrolysis, urticaria
- Endocrine & metabolic: Amenorrhea
- Gastrointestinal: Abdominal cramps, diarrhea, gastritis, gastrointestinal hemorrhage, gastrointestinal ulcer, nausea, constipation, flatulence, vomiting
- Genitourinary: Impotence, irregular menses, postmenopausal bleeding
- Hematologic & oncologic: Agranulocytosis, malignant neoplasm of breast
- Hepatic: Hepatotoxicity
- Hypersensitivity: Anaphylaxis
- Immunologic: DRESS syndrome
- Renal: Increased BUN, renal failure, renal insufficiency
- Miscellaneous: Fever

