9.3.2 Formulation of Control Product

There is no control product in this research protocol.

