12.2.1 Serious Adverse Experience Reporting

Adverse events will be documented per the University Hospitals Cleveland Medical Center, Human Research Protections guidelines, reported to the IRB, DSMB and the sponsor. The collection period for all SAEs will begin after informed consent is obtained and end after procedures for the final study visit have been completed.

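### Table 3 lets a known toxicity alone earn a *Definitely* related rating, and leaves some events with no rating at all

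*Combined protocol and SAP*

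**What the plan says.** Section 12.1 introduces the causality scale with the sentence "The relationship of an AE to the study drug should be assessed using the following the guidelines in Table 3". Table 3 has four rows.

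- *Definitely* begins "Previously known toxicity of agent; or an event that follows a reasonable temporal sequence from administration of the drug". The second alternative goes on to require a recognised response pattern and ends "that is confirmed by stopping or reducing the dosage of the drug; and that is not explained by any other reasonable hypothesis".
- *Probably* requires plausible timing, a recognised pattern, a positive dechallenge, and that the patient's condition or other treatment is an unlikely explanation.
- *Possibly* requires plausible timing and a recognised pattern, "but that could readily have been produced by a number of other factors".
- *Unrelated* is "An event that can be determined with certainty to have no relationship to the study drug".

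Table 3 speaks of one agent or drug, but every patient is to receive two, spironolactone and patiromer. Section 9.3.2 states "There is no control product in this research protocol", and section 9.2 says the study is not blinded. The side-effect lists in sections 3.1.1.1 and 3.1.1.2 include headache, lethargy, nausea, diarrhea, constipation and fever, as well as "Renal: Increased BUN, renal failure, renal insufficiency".

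**The concern.** A causality scale should ask for more evidence as the rating rises. Here the highest rating has a route that asks only what type of event occurred, while the two ratings below it both ask about timing.

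That matters more in this trial than in a controlled one. Entry under section 7.2 requires type 2 diabetes and reduced GFR, so renal deterioration and several of the non-specific symptoms will occur without any drug effect. With no comparator arm to show the background rate, the investigator's rating is one of the few means of separating drug effect from disease. If it can be set by event type alone, a count of *Definitely* related events may partly describe the population.

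The opposite end has a different problem. A new kind of reaction is what a safety assessment most needs to capture, yet the scale has no place for one unless it is certainly unrelated.

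**Working it through.** No rate or error probability enters the point, so the check is logical. All inputs come from Table 3. Write K for a previously known toxicity, T for plausible timing, P for a known or expected pattern, D for a positive dechallenge, and N for no other reasonable explanation.

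- *Definitely* = K or (T and P and D and N)
- *Probably* = T and P and D and other explanations unlikely
- *Possibly* = T and P and other factors could readily explain the event
- *Unrelated* = certainly no relationship

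Five kinds of event, as the table stands and after the K route is deleted with nothing else changed:

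| Event | Rows met now | Rows met with K deleted |
|---|---|---|
| 1. Known type, poor timing, no dechallenge, evident other cause | *Definitely*; *Unrelated* only if certain | None, unless certainly unrelated |
| 2. Known type and pattern, plausible timing, other ready causes, no dechallenge | *Definitely* and *Possibly* | *Possibly* |
| 3. Known type, all of T, P, D and N | *Definitely*, by both routes | *Definitely* |
| 4. No known pattern, good timing, positive dechallenge, no other cause | None | None |
| 5. Known type and pattern, plausible timing, drug never stopped or reduced, no other cause | *Definitely* | None |

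Four results follow.

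1. Event 1 fails *Probably* and *Possibly* on timing but meets *Definitely*. The order of evidence is reversed for it, and unless the investigator is certain of no relationship, no other row competes.
2. Event 2 meets two rows, and Table 3 has no rule for which prevails. The wording allows the higher rating but does not compel it.
3. Event 4 has no row, because every row except *Unrelated* needs either a known toxicity or a known pattern. Section 12.1 itself defines unexpected adverse events, so the plan foresees this kind of event.
4. Deleting the K route corrects events 1 and 2 and leaves event 3 where it belongs. It also leaves events 1 and 5 without a row, so the gap must be closed in the same edit.

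As to where the rating is used: sections 3.2 and 6.3 list laboratory change and incidence of adverse events, with no restriction to related events. Section 5 names serious hyperkalemia as the primary safety variable. Section 15 describes no analysis by relationship and leaves detail to a SAP still to be written.

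**The case against.** The strongest reply is that Table 3 is guidance for a clinician's judgement and not an algorithm. A creatinine rise on treatment in a patient with kidney disease is just what *Possibly* describes, and a sensible investigator would choose it. The phrase about toxicity of the agent can also be read as presupposing that the agent caused the event. Table 3 does not point to the side-effect lists in section 3; the only reference source section 12.1 names is the Investigator's Brochure, and that is for expectedness. The adverse event definition in section 12.1 already requires a temporal association with administration. Hyperkalemia is a poor example, because section 12.1 counts only potassium above 6.0 as an adverse event. And no stated endpoint or analysis uses the rating.

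Most of this stands, and it limits the point. A reader might infer that every background event of a listed type will be attributed to the drug. The documents do not support that: the table is guidance, *Possibly* overlaps with *Definitely*, and nothing gives *Definitely* precedence. A reader might also infer that the safety results as a whole are biased. That is not supported either, because overall incidence, laboratory change and serious hyperkalemia do not depend on the rating.

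The reply does not remove the defect. Judgement can resolve event 2, where two rows fit. It cannot resolve event 4 within the four definitions, and for event 1 the written guidance points to the wrong row. A general temporal association is also weaker than the timing condition that *Probably* and *Possibly* impose.

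**Conclusion.** The point holds as a defect in the definitions. Read literally, *Definitely* can be reached with less evidence than *Probably* or *Possibly*, so background events of known types can be over-attributed and the *Definitely* count inflated. Separately, an event that fits no known pattern and is not certainly unrelated cannot be rated.

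The effect is confined to the relatedness rating. Its size in patients cannot be stated, since it depends on background event rates and on how investigators read the row, and the documents give neither. The conclusion assumes only that the word *or* has its ordinary meaning. Section 12.1 calls for this rating and no control arm can check it, so the wording is worth correcting before the SAP is written. It does not threaten the efficacy results or the primary safety variable.

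**What to change.** Make three changes to Table 3.

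1. In the *Definitely* row, delete the stand-alone known-toxicity alternative, so that all four conditions already in the row are required together: plausible timing, a known or expected pattern, confirmation on stopping or reducing the drug, and no other reasonable explanation.
2. State that the rating is made separately for spironolactone and for patiromer.
3. Close the gaps. Dropping the known-pattern requirement from *Possibly*, and wording it as the row for any event with plausible timing that does not reach *Probably*, covers events 4 and 5. An *Unlikely* row covers event 1, where timing is poor but a relationship cannot be excluded with certainty.

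The cost is an edit to one table and its CRF code list, plus re-coding of events already rated; no new data are needed. Fewer events will carry the *Definitely* label, though all are still recorded and reported. The main drawback is that re-coding takes place in an unblinded study, with enrollment closed and the active participants already in the treatment phase (COVID-19 plan, section 11.3), so new ratings could be influenced by known outcomes. Keep the original ratings and report them alongside the revised ones.

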12.2 Serious Adverse Experiences (SAE)

An SAE is defined as any AE occurring at any dose that results in any of the following outcomes:

- death
- a life-threatening adverse experience
- inpatient hospitalization or prolongation of existing hospitalization
- a persistent or significant disability/incapacity
- a congenital anomaly/birth defect

Other important medical events may also be considered an SAE when, based on appropriate medical judgment, they jeopardize the subject or require intervention to prevent one of the outcomes listed.

12.2.1 Serious Adverse Experience Reporting

Adverse events will be documented per the University Hospitals Cleveland Medical Center, Human Research Protections guidelines, reported to the IRB, DSMB and the sponsor. The collection period for all SAEs will begin after informed consent is obtained and end after procedures for the final study visit have been completed.

12.3 Medical Monitoring

[name] and/or [name] should be contacted directly to report medical concerns or questions regarding safety.

13 DISCONTINUATION OF SUBJECTS

13.1 Early Discontinuation of Study Drug

A subject may be discontinued from study treatment at any time if the subject, the investigator, or the Sponsor feels that it is not in the subject's best interest to continue. The following is a list of possible reasons for study treatment discontinuation:

Subject withdrawal of consent (or assent)

Subject is not compliant with study procedures

Adverse event that in the opinion of the investigator would be in the best interest of the subject to discontinue study treatment

Protocol violation requiring discontinuation of study treatment

Lost to follow-up

Sponsor request for early termination of study

Positive pregnancy test (females)

If a subject is withdrawn from treatment due to an adverse event, the subject will be followed and treated by the Investigator until the abnormal parameter or symptom has resolved or stabilized.

All subjects who discontinue study treatment should come in for an early discontinuation visit as soon as possible and then should be encouraged to complete all remaining scheduled visits and procedures.

All subjects are free to withdraw from participation at any time, for any reason, specified or unspecified, and without prejudice.

Reasonable attempts will be made by the investigator to provide a reason for subject withdrawals. The reason for the subject's withdrawal from the study will be specified in the subject's source documents.

14 DATA SAFETY MONITORING

A Data Safety Monitoring Board (DSMB) will be established to review data relating to safety and efficacy, to conduct and review interim analyses, and to ensure the continued scientific validity and merit of the study. Reviews will be conducted by the DSMB every 3 months for the purpose of monitoring study conduct and assessing patient safety.

15 STATISTICAL METHODS AND CONSIDERATIONS

Prior to the analysis of the final study data, a detailed Statistical Analysis Plan (SAP) will be written describing all analyses that will be performed. The SAP will contain any modifications to the analysis plan described below.

General Statistical Considerations: All the tests are two-sided. We use log transformations for most continuous measures, and arc-sin square root transformations for percentages, both of which have excellent variance stabilizing properties for pooling variance.

16 DATA COLLECTION, RETENTION AND MONITORING

16.1 Data Collection Instruments

The Investigator will prepare and maintain adequate and accurate source documents designed to record all observations and other pertinent data for each subject treated with the study drug.

Study personnel at each site will enter data from source documents corresponding to a subject's visit into the protocol-specific electronic Case Report Form (eCRF) OR paper CRF when the information corresponding to that visit is available. Subjects will not be identified by name in the study database or on any study documents but will be identified by a subject number.

For eCRFs: If a correction is required for an eCRF, the time and date stamps track the person entering or updating eCRF data and creates an electronic audit trail. *For paper CRFs:* If a correction is made on a CRF, the study staff member will line through the incorrect data, write in the correct data and initial and date the change.

The Investigator is responsible for all information collected on subjects enrolled in this study. All data collected during the course of this study must be reviewed and verified for completeness and accuracy by the Investigator. A copy of the CRF will remain at the Investigator's site at the completion of the study.

16.2 Data Management Procedures

The data will be entered into a validated database. The Data Management group will be responsible for data processing, in accordance with procedural documentation. Database lock will occur once quality assurance procedures have been completed.

All procedures for the handling and analysis of data will be conducted using good computing practices meeting FDA guidelines for the handling and analysis of data for clinical trials.

16.3 Archival of Data

The database is safeguarded against unauthorized access by established security procedures; appropriate backup copies of the database and related software files will be maintained. Databases are backed up by the database administrator in conjunction with any updates or changes to the database.

At critical junctures of the protocol (e.g., production of interim reports and final reports), data for analysis is locked and cleaned per established procedures.

16.4 Availability and Retention of Investigational Records

The Investigator must make study data accessible to the monitor, other authorized representatives of the Sponsor (or designee), IRB/IEC, and Regulatory Agency (e.g., FDA) inspectors upon request. A file for each subject must be maintained that includes the signed Informed Consent, HIPAA Authorization and copies of all source documentation related to that subject. The Investigator must ensure the reliability and availability of source documents from which the information on the CRF was derived.

16.5 Subject Confidentiality

In order to maintain subject confidentiality, only a subject number will identify all study subjects on CRFs and other documentation submitted to the Sponsor.

17 ADMINISTRATIVE, ETHICAL, REGULATORY CONSIDERATIONS

The study will be conducted according to the Declaration of Helsinki, Protection of Human Volunteers (21 CFR 50), Institutional Review Boards (21 CFR 56), and Obligations of Clinical Investigators (21 CFR 312).

To maintain confidentiality, all laboratory specimens, evaluation forms, reports and other records will be identified by a coded number only. All study records will be kept in a locked file cabinet and code sheets linking a patient's name to a patient identification number will be stored separately in another locked file cabinet. Clinical information will not be released without written permission of the subject, except as necessary for monitoring by the FDA. The Investigator must also comply with all applicable privacy regulations (e.g., Health Insurance Portability and Accountability Act of 1996, EU Data Protection Directive 95/46/EC).

17.1 Informed Consent Form

Informed consent will be obtained in accordance with the Declaration of Helsinki, ICH GCP, US Code of Federal Regulations for Protection of Human Subjects (21 CFR 50.25[a,b], CFR 50.27, and CFR Part 56, Subpart A), the Health Insurance Portability and Accountability Act (HIPAA, if applicable), and local regulations.

A properly executed, written, informed consent will be obtained from each subject prior to entering the subject into the trial. Subjects will be given ample opportunity to inquire about details of the study. If a subject is unable to sign the informed consent form and the HIPAA authorization, a legal representative may sign for the subject. A copy of the signed consent form will be given to the subject or legal representative of the subject and the original will be maintained with the subject's records.

17.2 Publications

The preparation and submittal for publication of manuscripts containing the study results shall be in accordance with a process determined by mutual written agreement with the study Sponsor. The publication or presentation of any study results shall comply with all applicable privacy laws, including, but not limited to, the Health Insurance Portability and Accountability Act of 1996.

